8.0 DATA COLLECTION

All study-related data will be entered into OnCore. Access will be limited via a password known only to the investigator and designated research personnel (study nurse(s), data manager(s)).

9.0 STATISTICS

Statistical Considerations

The primary goal of this study is to compare and evaluate toxicities across four varied treatment schemes using a dose escalation design with four cohorts of 4-8 patients each. Escalation to the next dose will take place if no DLT's are observed in the first four patients treated at the current dose. If 2 or more DLT's are observed in the first four patients, then escalation is stopped. If 1 DLT is observed, then four more patients are treated at the same dose, and dose escalation stops if 2 or more of these next four (3/8 of patients treated at that dose) experience a DLT. If the probability of a DLT is 40%, there is a 71% chance of stopping at the current dose, whereas if the probability of DLT is 10%, there is only a 7% chance of stopping the dose escalation.

All analyses of the data will be descriptive. Clinical and radiographic efficacy will be summarized by calculating Kaplan-Meier curves for the following: overall survival, disease-free

survival, time to local progression, time to distant failure. Data from all dose groups will be pooled in these analyses. Survival rates estimated from the Kaplan-Meier curves will be estimated with 95% confidence intervals. Rates of acute and late side effects and adverse events will be summarized as proportions, with 95% confidence intervals.

Sample Size

The number of patients studied in this trial is determined by the dose escalation strategy and the number of DLT's that are observed at each dose level. With four dose levels and cohorts of 4-8 subjects per dose, the minimum sample size is 2 and the maximum is 32. It is expected that around 20 subjects will be enrolled. This design with cohort sizes of 4-8 per dose ensures that the probability of escalating to the next dose is .93 when the probability of DLT is .1, but is only .05 when the probability of a DLT is .6.

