2.0 OBJECTIVES

Primary objective: To evaluate and compare the clinical safety of utilizing four different schemes of radiosurgical ablative techniques for treating poor surgical candidates with renal tumors.

Secondary Objective: To evaluate and compare the clinical and radiographic efficacy of four different schemes of radiosurgical ablation of renal tumors in poor surgical candidates.

Serum Blood Marker Objective: To determine if serum markers collected before and after radiation may give a predictive indication of tumor response.

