3.0 PATIENT SELECTION

Conditions for Patient Eligibility

- Patient is considered a poor surgical candidate for removal of renal mass as determined by anesthesiology pre-operative assessment or the surgical team, or medical team. (No major psychiatric illnesses.)
- Patient is ≥ 18 years of age.
- Patient is able to give and sign study specific informed consent.
- No prior radiation to the treatment field.
- Negative serum or urine pregnancy test within 72 hours prior to registration for women of childbearing potential.
- Patient has a radiologically and /or pathologically confirmed diagnosis of a renal tumor
- Karnofsky status of $\geq 60\%$
- Signed study-specific informed consent prior to study entry.

All/any clinical, radiological and pathological data for the patient will be reviewed and the study investigators will assess suitability for treatment with radio-surgical technique. If the eligibility criteria are met, the patient will be scheduled for a treatment planning session.

Conditions for Patient Ineligibility

- Any patient not meeting the eligibility criteria.
- Any patient with active connective tissue disease such as lupus, dermatomyositis.
- Any patient with active Crohn's disease or active ulcerative colitis.
- Major psychiatric illness, which would prevent completion of treatment or interfere with follow-up.

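### Section 9.0 plans only Kaplan-Meier for time to local progression and time to distant failure and gives no rule for death without failure; on the natural reading, failure probabilities are overstated to an extent the documents cannot fix

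*Combined protocol and SAP*

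**What the plan says.** Section 9.0 (Statistical Considerations) gives one method for all the time-to-event efficacy endpoints: Kaplan-Meier curves for overall "survival, disease-free survival, time to local progression, time to distant failure". It adds that "Data from all dose groups will be pooled in these analyses", that "Survival rates estimated from the Kaplan-Meier curves will be estimated with 95% confidence intervals", and that "All analyses of the data will be descriptive".

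Neither Section 9.0 nor any other section says what counts as an event or a censoring for time to local progression or time to distant failure. Death without failure, competing risks and cumulative incidence are not mentioned.

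The setting is described elsewhere. The first eligibility condition in Section 3.0 is "Patient is considered a poor surgical candidate for removal of renal mass", and the same section admits Karnofsky status down to 60%. Section 7.0 sets follow-up at 36 months. Section 2.0 makes clinical and radiographic efficacy the secondary objective.

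**The concern.** Death makes later local progression or distant failure impossible, so for these two endpoints it is a competing event. If a patient who dies unfailed is censored, Kaplan-Meier treats that patient as someone who could still fail and gives the lost weight to those still alive. 1-KM then no longer estimates the proportion of treated patients who fail. It estimates a net rate, meaning failure in a setting without death, and does so only if death and failure are independent.

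The population makes this more than a formality. Patients enter because surgery is judged unsuitable and are followed for three years, so some deaths before any failure are plausible. Two of the four curves planned for the secondary objective could then be read as showing more failures than occurred. Overall survival is not affected, because death is its event.

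**Working it through.** **The plan's own figures.** Section 9.0 states no figure for these endpoints. Its only computed quantities are the stopping probabilities, and they reproduce. With P2 = P(at least 2 DLTs in 4) and P1 = P(exactly 1 in 4), P(stop) = P2 + P1 × P2. At DLT probability 0.1 this is 0.0523 + 0.2916 × 0.0523 = 0.068 (stated 0.07). At 0.4 it is 0.5248 + 0.3456 × 0.5248 = 0.706 (stated 0.71). They do not involve the efficacy curves.

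**Inputs from the documents.** Follow-up is 36 months (Section 7.0) and expected enrolment is about 20 (Section 9.0).

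**Inputs assumed.** Net failure *f* by 36 months is set at 10% and 30%, and net death without failure *d* at 20%, 40% and 60%. Hazards are constant and independent, and follow-up is complete. The documents give none of these as 36-month renal rates. The nearest anchors are a 93% control rate in a renal series with mean follow-up of 12 months (Section 1.0) and a 90% local control expectation for lung lesions (Section 6.0, Series II). The 30% has no source in the documents and only shows how the effect grows.

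**Formulas.** Let Hf = -ln(1-f) and Hd = -ln(1-d) be the cumulative hazards at 36 months.

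- 1-KM with death censored estimates f.
- The actual probability of failure is the cumulative incidence, CIF = Hf/(Hf+Hd) × [1 - (1-f)(1-d)].
- The standard error is approximated as SE = √(CIF × (1-CIF)/20).

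Example, f = 10% and d = 40%: Hf = 0.1054 and Hd = 0.5108, so CIF = 0.1710 × 0.46 = 7.9%. The excess is 2.1 points, the SE is 6.0 points, and the ratio is 0.35.

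Example, f = 30% and d = 40%: Hf = 0.3567, so CIF = 0.4112 × 0.58 = 23.8%, an excess of 6.2 points.

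| Net failure (1-KM) | Deaths | CIF | Excess, points | Excess / SE, n = 20 |
|---|---|---|---|---|
| 10% | 20% | 9.0% | 1.0 | 0.16 |
| 10% | 40% | 7.9% | 2.1 | 0.35 |
| 10% | 60% | 6.6% | 3.4 | 0.61 |
| 30% | 20% | 27.1% | 2.9 | 0.30 |
| 30% | 40% | 23.8% | 6.2 | 0.65 |
| 30% | 60% | 20.2% | 9.8 | 1.10 |

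At n = 32, the maximum in Section 9.0, the ratios rise by √(32/20) = 1.26; for example, 0.35 becomes 0.45.

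**Simulation check.** With n = 20 and failure detected only at six-monthly assessments, 10% net failure and 40% deaths gave mean 1-KM 0.101 against Aalen-Johansen 0.076 (SD of the latter 0.059). With 30% and 50% the means were 0.298 and 0.208 (SD 0.090). The gaps are slightly wider than the closed form gives, because some patients die before a failure is detected.

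**The other reading.** If death were counted as an event, the 10%/40% case would give 1 - 0.9 × 0.6 = 46% against a CIF of 7.9%. Kaplan-Meier would be a valid estimator of that composite, but the composite is not local progression or distant failure.

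**The case against.** The strongest reply is that the plan never says deaths are censored. What it shows is a missing definition, and the bias follows only on one reading of it. That is correct as to the text. But the alternative, counting death as an event, gives a composite that is further from a failure rate, so neither reading yields the probability of failure.

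A second reply is that 1-KM with death censored is a recognised measure of local tumour control when death and failure are independent. This also stands, and it is a reason to keep that curve as a supplement. The plan does not say a net rate is its target.

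A third reply is size. With 10% net failure, 20 patients and 40% deaths, the excess is 0.021 × 20 = 0.4 of one patient, below sampling error. This stands too, although the excess always has the same sign.

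Stronger readings are tempting, and the documents do not support them:

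- That deaths without failure will be common, or that the reported rates will be materially wrong. Frailty makes such deaths plausible, but no mortality figure is given.
- That 10% failure is the plan's own renal assumption. The figure behind it is for lung lesions.
- That published intervals for local and distant failure will be centred on the wrong value. The interval sentence speaks of survival rates and may cover only overall and disease-free survival.
- That these two curves are the core of the secondary objective. Survival curves are also planned, and Section 12.0 defines response categories.

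Patients who are re-treated leave the study (Section 7.0). That may be informative censoring, which Aalen-Johansen does not cure; it is a separate matter.

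**Conclusion.** The point holds in a limited form. Kaplan-Meier is the only method planned for the two endpoints, and death without failure has no rule. On the natural reading 1-KM overstates the actual probability of failure when such deaths occur. That direction does not depend on independence of death and failure, but the sizes in the table do, together with constant hazards, complete follow-up and assumed death rates. Over deaths of 20% to 60%, the range is about 1 to 3 points at 10% net failure and about 3 to 10 points at 30%. Because the analyses are secondary and descriptive and no DLT or escalation rule uses the curves, this is a change that should be made, not one on which the trial's conduct depends.

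**What to change.** In Section 9.0, state that death without the event is a competing event for time to local progression and for time to distant failure. Report Aalen-Johansen cumulative incidence for each, with pointwise 95% confidence intervals, for example at 12, 24 and 36 months. State the event and censoring rule for each endpoint. Keep Kaplan-Meier for overall survival, and for disease-free survival with death counted as an event.

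The cost is a sentence or two and a standard software routine. No new data are needed, because deaths must already be recorded for overall survival. The one small drawback is that the curves are less directly comparable with published Kaplan-Meier local control; that curve can be shown as a supplementary figure labelled as a net rate.

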5.0 REGISTRATION PROCEDURES

Approximately 32 subjects will be enrolled onto this study; four to eight individuals will be assigned to one of four different categories for comparisons to be made; an additional series of 12 patients will be enrolled in groups of 4 and assigned to three different categories. Patients can be registered only after the eligibility criteria are met. In addition, the following information must be provided:

- Patient's name and ID number.
- Verifying Physician's Name.
- Demographic Data.
- Treatment planning and start date.
- Eligibility criteria information.
- Patient's consent to enroll in the study
- All eligibility source documentation and checklist will be sent to the CTU QA office for review prior to subject enrollment

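### The efficacy objective asks for a comparison of schemes, but every planned efficacy curve pools all dose groups, so the comparative half of the objective has no analysis

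*Combined protocol and SAP*

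**What the plan says.** Section 2.0 gives the secondary objective as "To evaluate and compare the clinical and radiographic efficacy of four different schemes of radiosurgical ablation of renal tumors in poor surgical candidates". Section 11.0 likewise describes comparison of the four categories as a purpose of the study.

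Section 9.0 (Statistical Considerations) is the only analysis text. It describes a "dose escalation design with four cohorts of 4-8 patients each" and states "All analyses of the data will be descriptive". On efficacy it says "Clinical and radiographic efficacy will be summarized by calculating Kaplan-Meier curves for the following: overall survival, disease-free" survival, time to local progression and time to distant failure, followed by "Data from all dose groups will be pooled in these analyses". A later sentence says that rates of side effects and adverse events "will be summarized as proportions, with 95% confidence intervals".

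On numbers, section 9.0 says "It is expected that around 20 subjects will be enrolled", with a maximum of 32. Section 5.0 adds that "an additional series of 12 patients will be enrolled in groups of 4 and assigned to three different categories"; section 6.0 makes this Series II conditional on the toxicity seen in Series I. Section 12.0 (Response Criteria) defines response categories, but no section says how they will be analysed.

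**The concern.** A comparison, even a purely descriptive one, needs results shown by group. The pooling sentence rules that out for every efficacy endpoint, so this is more than a missing detail: the stated rule conflicts with the stated objective.

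The pooled curve also has no fixed target. Each level enrols four or eight patients, and later levels open or not, according to dose-limiting toxicities (DLTs). The toxicity results therefore decide how much each dose contributes to the efficacy estimate, and that estimate describes no particular dose. Without a prespecified by-level display, any comparison in the final report would be post hoc.

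**Working it through.** **1. The plan's own figures.** The documents give no sample size, power or effect size for efficacy, so there is no efficacy figure to reproduce. The only design calculation is the probability of stopping escalation: P(stop) = P(X≥2) + P(X=1)·P(Y≥2), with X and Y each binomial(4, p).
- p = 0.40: 0.5248 + 0.3456 × 0.5248 = 0.706 (stated 0.71).
- p = 0.10: 0.0523 + 0.2916 × 0.0523 = 0.068 (stated 0.07).

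These reproduce, but they concern DLTs only and do not bear on the efficacy comparison.

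**2. Objective against analysis.**

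| Section 2.0 asks for | Section 9.0 provides |
|---|---|
| An evaluation of efficacy | Pooled Kaplan-Meier curves for four endpoints with 95% intervals: served |
| A comparison across four schemes | No stratified curve, by-dose response table or contrast: not served |

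**3. The mixture.** Pooled control = Σ(nᵢ·cᵢ)/Σnᵢ. The control rates cᵢ = 60, 75, 90 and 95% at the four Series I levels are assumed for illustration. Censoring is ignored.
- Cohorts 4/4/4/4: (60 + 75 + 90 + 95)/4 = 80%.
- Lowest level expanded, 8/4/4/4: (480 + 300 + 360 + 380)/20 = 76%.
- Highest level expanded, 4/4/4/8: (240 + 300 + 360 + 760)/20 = 83%.
- Stopped at the second level, 4/4: (60 + 75)/2 = 67.5%.

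The spread is 83 − 67.5 = 15.5 points, produced by DLT counts alone.

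**4. How unlike the groups are.** Section 6.0 runs from 24 Gy in 4 fractions to 48 Gy in 4 (Series I: 4 levels), then to 60 Gy in 3 (Series II: 3 more levels), giving 4 + 3 = 7 regimens if Series II opens. The protocol names the linear-quadratic model but gives no α/β, so a range is shown. BED = nd(1 + d/(α/β)).

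| α/β (assumed) | 6 Gy × 4 | 12 Gy × 4 | 20 Gy × 3 | Series I ratio | Ratio with Series II |
|---|---|---|---|---|---|
| 10 | 38.4 | 105.6 | 180 | 2.75 | 4.7 |
| 3 | 72 | 240 | 460 | 3.3 | 6.4 |

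These ratios illustrate spread in dose. They do not measure error in the analysis.

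**5. What a by-level display could show.** Exact (Clopper-Pearson) 95% intervals, ignoring censoring:

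| Controlled | 95% interval |
|---|---|
| 3/4 | 19-99% |
| 4/4 | 40-100% |
| 7/8 | 47-99.7% |
| 8/8 | 63-100% |
| 18/20 pooled | 68-99% |
| 29/32 pooled | 75-98% |

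For a two-sided Fisher test at 0.05 (level and rates assumed), power for 90% against 60% control is 1.7% with 4 per group and 9.5% with 8 per group.

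**The case against.** The strongest reply is that this is a small dose-escalation study with descriptive aims. Pooling gives the only reasonably precise estimate, half of the objective is served, and dose and outcome are held per patient, so nothing is lost for good. By-level display could not reliably show that control rises with dose either, as step 5 confirms. All of this stands. It limits what a comparison can deliver and keeps the point modest, but it does not supply the comparison that the objective promises.

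A reader might be tempted to go further in four ways that the documents do not support:
- *That pooling distorts the recommended dose.* Section 6.0 ties the maximum tolerated dose to DLTs and the recommended Phase II dose to toxicity. No efficacy rule enters either.
- *That toxicity is pooled too.* The pooling sentence follows the list of efficacy curves and refers to those analyses. The toxicity proportions come afterwards, and DLTs are counted by level by design.
- *That the pooled curves certainly run up to 60 Gy.* Section 9.0 mentions four dose levels and never Series II. Including Series II in the pooled groups is a plausible inference only.
- *That a dose-trend model is needed.* It would depart from the descriptive plan. If the 93% control rate quoted in section 1.0 held, 20 patients would yield about 20 × 0.07 = 1.4 failures, with a chance of 0.93²⁰ + 20 × 0.07 × 0.93¹⁹ = 59% of none or one. A trend would be close to uninformative.

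**Conclusion.** The mismatch is real and rests on the text alone: the secondary objective promises a comparison of efficacy across schemes, and the only planned efficacy analysis removes it. The pooled curves remain valid as a description of the whole treated group, provided they are read as a mixture of doses.

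The size depends on unknown control rates. Under the assumed rates, the pooled figure moves by about 15 points across the four escalation paths with no change in efficacy at any dose. If control does not vary with dose, the mixture does no harm, but the plan has no display that would let a reader judge this.

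This should be corrected, at low cost. It affects a secondary, descriptive objective; it does not touch escalation, the primary safety objective or the data collected.

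**What to change.** Replace the pooling sentence in section 9.0 with text to this effect:

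1. Time to local progression (Kaplan-Meier) and best response will be shown descriptively by dose level, with numbers at risk and 95% confidence intervals. Deaths and patients taken off study for retreatment mean that a simple proportion controlled at a fixed time would mishandle censoring. Name an interval method that still works when a group has no failures, because the usual Greenwood interval then has zero width.
2. Where a failed Series II treatment plan lowered a patient's dose, both the assigned and the received level will be shown, since dose received is then related to anatomy.
3. Pooled curves will be kept as supportive and labelled a mixture of doses. Overall survival may stay pooled. State whether Series II is included.
4. Groups of 4-8 sequentially enrolled, non-randomised patients give wide intervals and do not support formal inference between doses.

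The cost is a few more tables and curves from data already collected, with no added patient, visit or procedure. The drawback is the width of the intervals, which the report must show. If by-level display is not wanted, the alternative is to remove the comparison from the efficacy objective in section 2.0 and align section 11.0. That restores consistency but gives up a stated purpose of the study.

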Twenty patients who are not surgical candidates will be offered treatment with a radio-surgical technique. Four patients will be registered in each dose group. Treatments will be initiated with 4 patients utilizing the minimum dose and observe what happens. If no DLTs are observed, then escalation to the next set of 4 patients to the next initial dose level will occur. If 1 DLT is observed, treatment of the next set of 4 patients at the same dose level will occur. If zero or 1 additional DLTs are observed, then dose escalation occurs as previously described. However, if $\geq 2/4$ or $\geq 3/8$ are observed at a given dose level the trial stops. On average, this results in between 4-5 patients being treated before escalation. The table below shows the probability of stopping giving an underlying toxicity level using this design.

Table: Probability of stopping escalation given underlying toxicity

Underlying Pr(Toxicity)	0.1	0.2	0.25	0.3	0.35	0.4	0.5	0.6	0.7	0.8	0.9
Pr(Stopping)	0.07	0.25	0.37	0.49	0.61	0.71	0.86	0.95	0.99	0.998	0.999

If a patient fails original treatment, he or she will be either kept on study for observation, or if they require retreatment, they will be taken off study.

Series II

The next series will be reached if insufficient dose limiting toxicities have occurred upon completion of the initial dose escalation series I to a total dose of 48 Gy in 4 fractions to warrant limitation of further dose escalation.

At this level, if normal tissue toxicities for SBRT have not proven to be problematic for renal lesions, then “standard” dose and fractionations will be prescribed for subsequent patients as would be used for example in Lung cancer. Given the 90% expectant local control for lung

lesions given 20 Gy in 3 fractions, we are highly anticipating reaching an efficacious dose during series II of the trial. If the 12 Gy x 4 fraction cohort is irradiated without dose limiting toxicities, then 12 additional patients will be accrued for further dose escalation following dose toxicity criteria defined below:

Based on the Linear Quadratic Model commonly used for radiobiologic comparisons, each subsequent group of four participants will receive further dose escalation using a 3 fraction regimen to increase beyond 48 Gy in 4 fractions in 20% dose equivalent increments.

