recurrence or progression, they will either be followed by observance; or if they require retreatment, they will be taken off study.

Radiation Toxicity:

All patients should be seen at 1, 3 and 6 months \pm 2 weeks, and then every 6 months by either the radiation oncologist or the urologist to evaluate radiation toxicities, or arranged to be seen locally if unable to return to Cleveland Medical Center with reports sent back for review. At 6 months post SBRT, the patient will be scheduled to be seen in Urology to evaluate their response to the therapy with imaging and an optional biopsy. Urinary and bowel irritation manifested as urgency, frequency, dysuria, infection and incontinence will be recorded. Medications to treat radiation side-effects will be recorded as well as dose and frequency. Acute Radiation Toxicity (<180 days from treatment date) will be documented using NCI common toxicity criteria, version 4.0. A shorter period of toxicity assessment for the purposes of dose escalation will be used. This will be done at the 1, 3 and 6 month follow-up visits after radiation therapy. More delayed short-term toxicities would be used in the final determination of the recommended Phase II dose.

Dose limiting Toxicity:

Acute Radiation Toxicity \geq grade 3 in the Gastrointestinal and renal/genitourinary categories of the common terminology criteria for adverse events 4.0 (CTCAE) will be considered dose limiting (see above). The maximum tolerated dose will be one dose level below which the adverse event, as described above, occurred (See statistical section).

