7.0 PATIENT ASSESSMENTS

Follow-up schedule and parameters assessed will be as follows:

		Treatment			Months Post-RT							
Parameters	Screening	Dose 1	Dose 2	Dose 3	1	3	6	12	18	24	30	36
History & Physical	X				X	X	X	X	X	X	X	X
Pregnancy Test	X											
Toxicity Evaluation					X	X	X	X	X	X	X	X
Biopsy	X						X ²					
MRI or CT of chest and Abdomen	X						X	X	X	X	X	X
Radiotherapy		X	X	X								
ELISA Blood Draws ¹		X ¹	X ¹	X ¹								

¹ To be drawn within 2 hours prior to and following completion of fractionated radiation therapy

² Patient will be given the option to have this procedure between 6 to 12 months follow up post RT. Standard stains with H & E as well as any staining to assess tissue viability will be ordered as available to possibly include NADH

(marker of metabolism) and MIB-1 (proliferation marker) or propidium iodide, which is a marker of cell membrane integrity and thus, death.

Post-Treatment Follow-up Schedule

After radio-surgery, follow-up will be done at 1, 3 and 6 months and then every 6 months post radiosurgery for a total of 36 months.

If viable tumor is identified or enhancement on any post therapy follow-up CT or MRI is identified, the patient may be offered additional treatment or observation, based on imaging analysis or patient preference and co-morbid illness clinical status. If the patient receives any re-treatment, they will be taken off study.

Radiation treatments for this subject will cease if any DLT's occur. The patient will then be followed every 6 months until 36 months after the radiation treatment.

Between 6 to 12 months following the end of RT, an optional percutaneous renal biopsy of the target tumor under US or CT guidance will be offered.

Acute vs. Late Toxicity

Acute toxicity monitoring: Acute side effects (\leq 180 days from RT start) will be documented using the using the NCI Common Toxicity Criteria version 4.0. (CTCAE)

Late toxicity monitoring: All late ($>$ 180 days from RT start) side effects will be evaluated and graded according to the. NCI Common Toxicity Criteria version 4.0. (CTCAE)

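### Late toxicity is planned as a simple proportion although late events accrue to month 36 and follow-up can end early; the denominator is undefined, and its choice decides the direction of the bias.

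*Combined protocol and SAP*

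**What the plan says.** Section 9.0 (Statistical Considerations) gives one rule for all toxicity: "Rates of acute and late side effects and adverse events will be summarized as proportions, with 95% confidence intervals". It names no denominator, no time point for the late rate and no handling of patients with less than full follow-up. The same paragraph treats efficacy differently: "Clinical and radiographic efficacy will be summarized by calculating Kaplan-Meier curves for the following: overall survival", followed by disease-free survival and the times to local progression and distant failure. It also says "All analyses of the data will be descriptive".

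Section 7.0 defines late toxicity as side effects arising more than 180 days from the start of radiotherapy. Visits continue "every 6 months post radiosurgery for a total of 36 months".

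Follow-up can stop before then. Section 7.0 states "If the patient receives any re-treatment, they will be taken off study", and section 6.0 has the same rule: "if they require retreatment, they will be taken off study". No toxicity assessment is described after a patient goes off study.

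**The concern.** The late window runs for about 30 months. A proportion is a clean estimate of 36-month risk only if everyone without an event is watched to month 36 or has died, with death regarded as a competing event. Here the protocol removes re-treated patients, and loss or withdrawal can occur in any trial. The plan uses a method that handles incomplete follow-up for all four efficacy endpoints, but not for late toxicity, although safety is the primary objective (section 2.0).

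At stake is the late-toxicity rate that readers will take from the trial. Because the denominator is open, two analysts following section 9.0 could report rates biased in opposite directions, each with a confidence interval around the wrong value.

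**Working it through.** **The plan's own figures.** The only computable figures in section 9.0 are the stopping probabilities. Pr(stop) = P(X ≥ 2 of 4) + P(X = 1 of 4) × P(Y ≥ 2 of 4).

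- DLT probability 0.10: 0.0523 + 0.2916 × 0.0523 = 0.068 (stated 0.07).
- 0.40: 0.5248 + 0.3456 × 0.5248 = 0.706 (stated 0.71).
- 0.60: 0.8208 + 0.1536 × 0.8208 = 0.947, so escalation 0.053 (stated 0.05).

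These reproduce. They concern acute DLTs and say nothing about late toxicity, for which the documents give no rate.

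**Inputs.**
- Late window: after day 180 to month 36, about 30 months (section 7.0).
- True 36-month late-toxicity risk T: assumed 20%.
- Share c leaving early by loss, withdrawal or re-treatment: assumed 10% to 50%.
- Constant hazards, with leaving independent of toxicity: assumed.

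**Formulas.** With h = −ln(1−T)/30 and g = −ln(1−c)/30:
- All-treated denominator: A = h/(h+g) × [1 − (1−T)(1−c)].
- Denominator of patients with an event plus those who complete 36 months: B = A / [A + (1−T)(1−c)].

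**Example, c = 30%.** −ln 0.8 = 0.2231 and −ln 0.7 = 0.3567, so h/(h+g) = 0.2231/0.5798 = 0.385. (1−T)(1−c) = 0.56. A = 0.385 × 0.44 = 0.169. B = 0.169/(0.169 + 0.56) = 0.232.

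| Leaving early | All treated (A) | Relative shortfall | Events plus completers (B) |
|---|---|---|---|
| 10% | 19.0% | 5% | 20.9% |
| 20% | 18.0% | 10% | 22.0% |
| 30% | 16.9% | 15% | 23.2% |
| 40% | 15.8% | 21% | 24.8% |
| 50% | 14.6% | 27% | 26.8% |

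If leaving starts at month 0 rather than month 6, A runs from 18.8% (10% leaving) to 13.7% (50% leaving), a shortfall of up to 32%. The relative shortfalls are nearly the same at true risks of 10% and 30%.

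**Deaths.** If the early exits are deaths and the target is cumulative incidence with death as a competing event, formula A is that target. With 30% deaths both equal 16.9%, so the all-treated proportion is unbiased. Censoring the deaths in a Kaplan-Meier estimate would give 20%, which overstates this quantity. The same reasoning applies to re-treatment if it is defined as a competing event, so the plan has to say which it is.

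**Sampling error.** Section 9.0 expects around 20 subjects. The exact 95% interval for 4/20 is 5.7% to 43.7%; for 1/4, one cohort, it is 0.6% to 80.6%.

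**The case against.** The strongest reply is that this is a small descriptive study. Escalation and stopping depend on acute toxicity of grade 3 or higher, so the late rate drives no decision rule. The bias shown, about 1 to 6 percentage points, is well inside the sampling error. The documents give no loss rate, and several provisions keep patients under observation: those with a DLT are followed to 36 months, and patients whose tumour fails may stay on study for observation. All of this stands, and it limits the weight of the point. It does not supply a denominator, and a wide interval is no reason to leave the estimated quantity undefined.

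Some stronger readings are tempting and should not be drawn.

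- A reader might infer that every early leaver counts as free of late toxicity. Section 9.0 does not say so. It would follow only from an all-treated denominator, and even then a patient with a late event before leaving is counted.
- A reader might infer that patients who die are wrongly counted. With death as a competing event they belong in the denominator without an event.
- A reader might infer that the later, higher dose cohorts would look safest because they have been followed for less time. That needs an analysis before the last cohorts reach month 36. Follow-up is fixed at 36 months per patient, and section 9.0 schedules no earlier late-toxicity analysis.
- A reader might take the provision in section 6.0 for patients to be "arranged to be seen locally if unable to return to Cleveland Medical Center" as a sign of loss. That sentence goes on to require reports back for review, so it is a means of keeping follow-up.

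**Conclusion.** The point holds in a limited form. A simple proportion is the wrong summary for late toxicity when follow-up can end early, and here the protocol's own re-treatment rule makes it unequal. The direction of the bias is not fixed by the documents: downward with all treated patients if exits by loss, withdrawal or re-treatment are regarded as censoring, and upward with completers and events only. At an assumed 20% risk with 10% to 50% leaving early, the two choices give 19% to 15% and 21% to 27%.

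These sizes rest on assumed risk and exit rates, constant hazards and independent exits. Independence is least secure for re-treatment, which follows tumour failure. Acute toxicity, with its 180-day window, is much less exposed. The consequence is confined to the descriptive late-safety estimate. The change is worth making because it is specific and cheap and concerns the primary objective; it does not undermine the escalation design.

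**What to change.** In section 9.0:

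- Keep simple proportions with 95% confidence intervals for acute toxicity.
- Report late toxicity as cumulative incidence at 12, 24 and 36 months from radiotherapy, with 95% confidence intervals. Treat death as a competing event and loss or withdrawal as censoring.
- Censor at re-treatment, and add a sensitivity analysis with re-treatment as a competing event.
- Give the number still followed at each time, by dose level.
- Keep crude counts as description only, with the denominator stated.

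This needs SAP wording and a little programming; visit, toxicity and survival dates are already needed for the planned analyses. The downside is slightly wider intervals and a possibly less favourable late-toxicity rate.
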